Collective action	enacting	understanding the experience with the CEC in terms of facilitators, problems, and perceived outcomes
Reflexive monitoring	Appraisal	Critical appraisal on the service delivered and further suggestions to improve CEC

The interview's topic guides are reported in Appendix 1. Specific interview questions were designed for - Local Managers/Heads of Departments; CEC's member; HPs who submitted an ethics consultation request.

Participants' informed consents to the study and data treatment, and interviews' transcription will be collected and archived by a Smarty Web, an online tool provided by the Local Health Authority of Reggio Emilia to collect and archive the personal data of participants involved in research activities.

Evaluating a Clinical Ethics Committee (CEC) implementation process in an Oncologic Research Hospital. A process evaluation study using Normalization Process Theory .

1) Cognitive survey

To identify factors which might shape the implementation of CEC, we design, pilot and disseminate an online survey through HPs who attended at least 1 of 5 training course on clinical ethics promoted by the CEC. The survey will be developed using a modified version of the NoMAD instrument (based on NPT) and will explore attitudes to the prospect of the development of the CEC at the Local Health Authority of Reggio Emilia (the tool is provided in Appendix 2).

We chose the NoMAD tool as it is the first quantitative measure based on NPT. NoMAD can be used to describe participants' views about how an intervention impacts on their work, and their expectations about whether it could become a routine part of their work and as a way of improving implementation by identifying areas needing further work to progress an implementation project. The survey is composed by 20 implementation assessment items reflecting the constructs of NPT, from the professionals directly involved in the work of implementing complex interventions in healthcare (Finch 2013).

We used the NoMad Italian validated version available at : https://www.implementall.eu/NoMAD_Italian.pdf

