According with the italian version provided, any personal data is included in the survey, which is completely anonymous. The developers suggest adapting and customize the tool for specific use by replacing the word "intervention" with a term that would be more familiar to study participants [Finch 2013]. For this study, "intervention" will be replaced with "Comitato per l'Etica nella clinica (CEC)."

Finally, the survey will be integrated with open questions free text to assess acceptability of elements of the CEC, including activities performed, the process of working with CEC and further improvements for the CEC developments.

The survey will be developed with Google Form with multiple options and the following open-ended questions:

How can this CEC be improved?

What issues would you like to address in a future CEC?

What has CEC brought to the health care facility?

Do you have other general/supplemental remarks?

Open ended questions will elicit HPs' views on their opinion, experience with the CEC and expectations.

The surveys' results will be collected in the related Microsoft Excel.

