5.3.3. Data Analysis

Semi-structured interview

Interviews will be audio-recorded and transcribed verbatim.

Data analysis will be conducted by two researchers with experience in qualitative research. Interviews' transcriptions and free text from qualitative survey will be analyzed using thematic analysis [Braun 2006], whose analytical stages can be summarized as follows:

- Each researcher will read the transcriptions and write comments and initial thoughts in a memo.

Evaluating a Clinical Ethics Committee (CEC) implementation process in an Oncologic Research Hospital. A process evaluation study using Normalization Process Theory .

- Each researcher will extract portions of the text individually and then share their work to reach an initial agreement. During this stage, they will conduct the thematic analysis inductively [Braun V 2006] providing their insights.
- Researchers will independently review themes and allocate portions of the text to the newly reconfigured themes.
- Together, they will re-define themes and re-name them to achieve internal consistency.
- One researcher will extract from the interviews and draft the final report, which will be checked and amended by the other two.

The methodological rigor of the analysis will be further guaranteed by the supervision of a third, independent researcher.

After a first, inductive analysis of qualitative data, the construct of NPT will be applied to the emerging themes to interrogate, challenge, confirm or refine the themes. (McNaughton 2020).

Cognitive survey

The quantitative data collected by cognitive survey will be represented using descriptive techniques; that is, they will be summarized in terms of frequency and percentages for categorical variables, mean and standard deviation for symmetric quantitative variables and median and IQR for the remaining ones.

Free text from surveys will be analysed by thematic analysis described.

The study will be developed within 10 months since the CE AVEN approval.

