This survey is designed to better understand how to apply and integrate complex interventions into daily clinical practices. Specifically, this survey asks questions about the implementation process of the Clinical Ethics Committee (CEC) at the Local Health Authority of Reggio Emilia.

The survey is composed by 2 parts. The first part contains a series of more detailed questions about the implemented intervention through closed-ended questions. The second, on the other hand, contains some open-ended questions concerning some aspects of this intervention. Please take the time to decide which answer best fits your experience for each statement and check the appropriate box.

This Survey was developed following the model of Finch, T.L., Girling, M., May, C.R., Mair, F.S., Murray, E., Treweek, S., Steen, IN, McColl, E.M., Dickinson, C., Rapley, T. (2015). Nomad: mplementation measure based on Normalization Process Theory. [Measurement instrument]. Accessed at: <http://www.normalizationprocess.org>.

[figure not shown]
**Evaluating a Clinical Ethics Committee (CEC) implementation process in an Oncologic Research Hospital. A process evaluation study using Normalization Process Theory .
Version 1, December 23, 2021**

n.	Question	Agree	Partially Agree	Neutral	Partially disagree	Disagree
1	I'm able to distinguish CEC from the usual hatreds of working					
2	Staff in this organization have a shared understanding of the purpose of CEC					
3	I understand how CEC affects the nature of my work					
4	I am able to see the potential value of CEC to my work					
5	There are managers in place to ensure the delivery of the intervention and to engage other practitioners					
6	I believe that participating in the dissemination of the CEC is a legitimate function of my role					
7	I am willing to work in new ways with my colleagues to use CEC					
8	Continuerò a supportare l'utilizzo del CEC					
9	I will continue to support the use of CEC					
10	Turning to CEC disrupts working relationships					
11	I have confidence in the ability of other practitioners to use CEC					
12	The work is assigned to professionals who possess adequate skills to use CEC					
13	Sufficient training has been provided to enable staff to implement CEC					
14	Sufficient resources are available to support the delivery of CEC					
15	Management adequately supports the delivery of the ECC					
16	I am aware of scientific reports on the effects of CEC					
17	Staff agree that using CEC is fruitful.					

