18	I appreciate the effects the delivery of CEC has had on my work					

**Evaluating a Clinical Ethics Committee (CEC) implementation process in an Oncologic Research Hospital. A process evaluation study using Normalization Process Theory .
Version 1, December 23, 2021**

19	It is possible to use the feedback collected on the CEC to improve the tool in the future					
20	I can modify the way I work with the CEC					
A	In what ways can the CEC be improved??					
B	What aspects would you like CEC to address in the future?					
C	What has CEC brought to the health care facility where you work?					
D	Do you have additional opinions and/or suggestions with respect to the way this service operates?					

**SERVIZIO SANITARIO REGIONALE
EMILIA-ROMAGNA**
Azienda Unità Sanitaria Locale di Reggio Emilia
IRCCS Istituto in tecnologie avanzate e modelli assistenziali in oncologia

**Evaluating a Clinical Ethics Committee (CEC) implementation process in an Oncologic Research Hospital. A process evaluation study using Normalization Process Theory .
Version 1, December 23, 2021**

Normalization Measure Development Questionnaire (short NoMAD)

(Adapt the questionnaire to your purposes by specifying [the intervention] you are using inside the brackets)

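### Items 8 and 9 of the Appendix 2 survey are the same statement, so the printed tool has 19 distinct closed items, not the stated 20

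*Combined protocol and SAP*

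**What the plan says.** The Cognitive survey part of section 3 (Materials and Methods) gives the number of closed items: "The survey is composed by 20 implementation assessment items reflecting the constructs of NPT". The same section says that "the tool is provided in Appendix 2" and cites a validated Italian version as the source.

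The section describes two adaptations. The first concerns wording: "The developers suggest adapting and customize the tool for specific use by replacing the word" that stands for the intervention, here with the committee's name. The second is an addition: "the survey will be integrated with open questions free text to assess acceptability of elements of the CEC". Neither removes or repeats a closed item.

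Appendix 2 prints a table of closed statements numbered 1 to 20, followed by open questions A to D. Row 8 is "Continuerò a supportare l'utilizzo del CEC". Row 9 is "I will continue to support the use of CEC". The last numbered row, 20, is "I can modify the way I work with the CEC".

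For the analysis, section 5.3.3 says: "The quantitative data collected by cognitive survey will be represented using descriptive techniques". It names frequencies and percentages, means with SD, and medians with IQR. It defines no composite or construct score.

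**The concern.** Row 9 is the English translation of row 8. Because each has its own number and the sequence still ends at 20, the repeat takes the place of one intended item.

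NoMAD is included to show where implementation needs more work, and its results will be reported descriptively. A missing item is therefore a missing result, and a repeated item is a redundant one.

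The gap would be hard to close properly afterwards. Under the recruitment procedure for this survey, invitations go out through the Training Office, responses are anonymous, and collection ends after one invitation and one reminder. Answers to an item sent later could not be linked to the respondents who completed the first form.

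**Working it through.** This is a count, so no sampling or error-rate calculation applies.

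**Inputs**
- Closed items stated: 20 (section 3, Cognitive survey).
- Numbered closed rows printed: 1 to 20 (Appendix 2).
- Open questions listed: 4 (section 3, Cognitive survey). Open rows printed: A to D (Appendix 2).
- Response window: two weeks, then one more week after the reminder (Recruitment Procedure, cognitive survey).

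**Step 1: reproduce the stated figure.** Numbered rows = 20. This matches the text if rows are counted without reading them.

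**Step 2: count distinct statements.** With row 8 translated, all 20 statements were compared in pairs. Rows 8 and 9 are identical (text similarity 1.00). The next closest pair, rows 14 and 15, scores 0.59 and asks about different things: resources and management support. There is therefore one duplicate.

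- Distinct closed items = 20 − 1 = 19
- Shortfall = 20 − 19 = 1 item, and 1/20 = 5%

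**Step 3: check the open part.** Four questions are listed and four are printed, so the shortfall is 0. The whole form has 20 + 4 = 24 rows, of which 19 + 4 = 23 are distinct. The gap is confined to the closed part.

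**Step 4: look for an explanation in the plan.** Replacing a word does not change the number of items. Adding open questions affects only rows A to D. Neither accounts for the repeat.

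**Step 5: range of consequences**

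| Situation | Items not measured | Statements tabulated twice |
|---|---|---|
| Form fielded as in Appendix 2 | 1 of 20 (5%) | 1 |
| Italian online form intact | 0 | 0 |

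**Step 6: time in which to notice.** 2 + 1 = 3 weeks from first invitation to close.

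**The case against.** The strongest reply is that Appendix 2 is probably not what respondents will see. The protocol says the Italian version is used, and the appendix is clearly a rough English rendering: row 1 is mistranslated, row 15 has a different abbreviation for the committee, and row 8 was left in Italian. A translation or editing slip is a plausible explanation, and the fielded form may have 20 distinct items. The appendix also ends with a heading for the short NoMAD, and whatever followed it is not available here. It may have been the source questionnaire.

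The protocol also calls the tool a modified version and plans a pilot, which could well reveal two identical adjacent statements. No score depends on the item. An omitted item could be sent again by the same route and tabulated separately, though possibly to a different set of responders.

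Most of this stands as a limit on the consequence. The documents do not establish that any data will be lost, and they cannot identify the displaced item. But the general description as modified does not explain a duplicate when the text still gives 20 items. The pilot may catch the repeat, yet no check of the form against the cited version is described. Even if the online form is sound, Appendix 2 is the tool the protocol refers to, and it disagrees with the stated count.

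**Conclusion.** The concern holds for the tool as printed: 19 distinct closed items against 20 stated, with rows 8 and 9 the only identical pair. The separate row numbers rule out a fault in reading the PDF.

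The possible loss is between 0 and 1 of 20 items (0% to 5%). The upper end assumes that the online form copies Appendix 2, and the lower end assumes that it follows an intact Italian version. The documents do not settle which. Study validity is not at risk and no planned summary score is distorted. The point is still worth correcting before launch because the error is certain on the page, a missed item could not be added later for the same respondents, and the remedy is trivial.

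**What to change.** Before launch:

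1. Compare Appendix 2 and the Italian online form, row by row, with the Italian NoMAD version cited in the Cognitive survey section.
2. Replace the repeated row with the omitted item in Appendix 2 and, if it has the same fault, in the online form, so that 20 distinct closed items are fielded.
3. In the same edit, put the committee's name into row 5, which still uses the generic term that the protocol says will be replaced.

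The cost is one check and a one-row replacement, plus the wording change in row 5. Respondent time does not increase, because one row replaces another, and the design and analysis are unchanged.
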